Another strategy for recruitment that avoids relying on adolescents to transport paperwork is the use of email communication with parents. Principals at participating schools send regular updates to parents and have included an introduction to our projects with a link to a REDCap page for parents to electronically complete the consent to contact form that allows project staff to contact them with details about the project.

Finally, project staff recruit at school events attended by parents (open houses, awards nights, school plays, sporting events, etc.). Again, having a presence at events where some families have previously participated in the project and spontaneously refer other parents to the project table has proven beneficial to recruitment.

Recruitment is also enhanced by the respect for participants that is a core component of the training received by research assistants responsible for interactions related to recruitment. Families are encouraged to take time to discuss the project and to ask questions at all phases, including when deciding whether to schedule a consent appointment. Respect for families' time is conveyed by the reimbursement schedule that compensates both adolescents and parents separately for the time invested in completing assessment procedures for the project. Respect for school procedures and personnel has also fostered positive, ongoing relationships between our research lab and the local school districts; these supportive relationships enhance collaborative problem solving around recruitment when issues arise.

Health Education Professionals Panel (HEPP) Recruitment: Health teachers and other school health professionals (e.g., nurses, counselors) will be recruited (n=8) for the HEPP to advise on the adaptation of the TRAC intervention during Phase 1. School staff directly involved in health of middle school students at each participating school, in addition to school health personnel who are members of the Rhode Island Department of Health (RIDOH) school nurses listserv and representatives of the Planned Parenthood Federation of America, will be invited to participate in the panel meetings during Phase 1. Staff will be contacted through the RIDOH listserv or through their publicly available organization or school district email accounts, a strategy that has been successful in our current research.

Intervention Retention: After families are enrolled in the project, retention to completion of the intervention will be critical to assessing its efficacy. The pilot trial showed excellent retention to the intervention, with 88% of adolescents randomized to the intervention condition completing all 4 sessions of the intervention. For the group-based format of TRAC, average attendance was 75%.

Several strategies will be used to engage and retain participants in iTRAC-SRP.

1) iTRAC was designed with intervention retention in mind by emphasizing an interactive gaming approach to the intervention that is appealing to adolescents and encourages participants to complete the program.

2) "Badges" are awarded for completing activities in the program. Used in the pilot with success, these badges are given names that reflect the construct of the game but are also engaging (e.g., "Emotion Commotion," "Truth Sleuth"). They mark progress through the program, and a tally of badges earned is noted in the upper corner of the game. Other in-program reinforcers will be employed in the complete program, such as virtual prizes (e.g., dressing up their character in the game) that enhance connection and individualize experience with the program.

3) Retention to the intervention is enhanced by the health content of iTRAC-SRP, especially the topics of relationships and sexual health. These topics are of interest to early adolescents, who anecdotally complain that information received in health class regarding sex and relationships is inadequate. In addition, the program teaches strategies for managing emotions that often interfere with relationships for early adolescents, thus creating interest in learning more through continued participation in the intervention.

4) Adolescents complete the interventions in locations convenient, familiar, and comfortable for them. As in the pilot, sessions will be held immediately after school at the school (e.g., library or classroom; all schools have procedures allowing project staff to use their facilities after hours). This makes attendance for students feasible and convenient. Accommodations can be made for students who have after school commitments, though these are rarely daily events at this developmental stage. Alternative locations can include the local library (all

local libraries have rooms that can be reserved for privacy of assessment or intervention procedures), adolescents' homes (staff travel in pairs to ensure safety), and the research office.

5) Providing families with flexibility in timing of appointments is maintained as a priority by project staff. Several days each week will be offered for program completion right after school. This flexibility is an advantage over group-administered interventions, which are restricted to a specific time and can lead to missed content when participants miss group. Mobile formats allow participants to receive 100% of the content at their own pace.

6) Reminders will be sent via text messages to parents (and adolescents who have phones and permission to receive texts from research staff) regarding scheduled appointments to complete intervention sessions.

7) Snacks will be provided. Work from our previous trials has shown that hunger can lead adolescents to leave school at the end of the day; providing snacks reinforces attendance and focus.

Follow-up Retention: Retaining participants for follow-ups is critical to assessing efficacy. The PI has demonstrated strong retention to study completion with challenging populations in other studies (e.g., middle schoolers with mental health symptoms: 85% at 30-month follow-up (R01 NR011906); dyads of adolescent boys and their parents: 88% at 9-month follow-up (2014-MU-CX-0002). Similarly, the pilot study of iTRAC retained 94% of adolescents for the final assessment (3-months). We will facilitate retention over the proposed 6-month follow-up using successful procedures from our own studies and the literature.

1) Seventh graders attend 8th grade in the same middle schools, which facilitates tracking.

2) Compensation to families conveys respect for participant time and effort. Adolescents will receive \$50 for completing assessment procedures at each time point (baseline, post-intervention/2-month, and 6-month follow-up) to convey the importance and value of completing the project. Parents will receive \$30 for each of their assessments (baseline and 6-month follow-up) which involve less time than adolescent assessments.

3) The informed consent process is an opportunity to educate participants about the importance of data collection to research studies. To motivate collaboration, families will be educated during the consent process as to why completing the intervention (if randomized to iTRAC-SRP) and follow-up assessments is important to the research and problem solve any anticipated barriers to participation.

4) Each school will have a dedicated research assistant who will assume primary responsibility for recruitment and tracking of participants at that school. In this way, participants have a primary project contact who will conduct project activities with the family over time to develop rapport with families. This encourages familiarity and comfort with the project and, in turn, retention.

5) Follow-ups will be conducted at locations convenient to families (see Intervention Retention, item 4). The vast majority of adolescents prefer to complete study activities at school. However, alternative locations can include the local library, adolescent's home, or the research office. All assessment procedures can be completed in any of these locations, due to the portability of study devices.

6) Parent assessments will be brief (15-20 minutes) and follow-ups can be completed by email or phone.

7) To limit barriers to families of diverse cultural backgrounds, all parent materials (consents, questionnaires) will be available in Spanish, and at least one Spanish-speaking RA will be a part of the staff.

8) Other mailings, such as holiday cards are sent to enhance recall and familiarity with the project.

9) Standard assessment procedures include research assistants providing appointment reminders by phone/text and providing scheduled appointments in writing. Standard lab procedure also includes inquiring about anticipated moves or phone number changes, to avoid challenges in reaching families for follow-ups. In the unusual circumstance in which a family moves out of the range in which a research assistant can conduct an in-person assessment, the questionnaire portion of the battery can be emailed to adolescents via REDCap.

10) Families complete locator forms that provide contacts who can help staff locate the family if their contact information changes. These forms are completed at each assessment point and include a check box and signature procedure for parents to permit schools to provide updated contact information as well.

HUMAN SUBJECTS RESEARCH

This study is nonexempt research involving human subjects. Rhode Island Hospital (FWA#00001230) will provide the oversight IRB for the study. Approval for the project and for consent forms will be obtained from the Rhode Island Hospital Institutional Review Board.

PROTECTION OF HUMAN SUBJECTS

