Deliverable: A summary report of quantitative and qualitative data from the Acceptability testing questionnaires and interviews will accompany a table of recommended changes that will guide Klein Buendel's revisions to the program, leading to the finalized iTRAC-SRP program.

Phase 2c- Randomized Control Trial (months 19-36): **Recruitment:** For the RCT, project staff will recruit 120 7th grade students from two waves of enrollment over an eight-month period that will span across two school years, providing two unique cohorts of 7th graders from which to recruit. We will examine sample demographics after the first cohort to ensure diversity in terms of race, ethnicity, and SES. Oversampling will be conducted if sampling is not representative of diversity at the schools, though our previous projects have not experienced this. Participants will be recruited through several methods consistent with those used to successfully recruit in the pilot trial and in our other school-based studies (see **Form F- Recruitment and Retention**). 1) Students will be introduced to the program at school via small-group presentations emphasizing the content (sexual and

emotional health) and approach (gaming), both of which are of interest to this age group. The introductions will be conducted by project staff, who will distribute flyers with QR codes that connect to a REDCap link to the “consent to contact” form, to avoid students having to remember to return the form. Parents can also sign and return the forms to the school. 2) Principals will introduce the project to parents via school announcement emails that contain the REDCap link to the consent to contact form. 3) Project staff will recruit at school events attended by parents (open houses, sporting events, etc.).

Once permission to contact the family is received, trained staff arrange a meeting to describe the project, obtain parental consent, and complete baseline parent measures. Separate meetings for adolescents are arranged to explain the project and obtain assent (separate from their parent). The Translation and Acceptability stages will also use the classroom recruitment procedures described above. Parents and teens will be compensated for time and effort in all stages of the project.

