Randomization: Participants will be individually randomized to either iTRAC-SRP or waitlist control after baseline, following consent. Per recommendations for achieving between-group comparability in clinical trials,¹⁰⁵ randomization will be stratified by school and gender and blocked using predetermined size-4 blocks. Individual randomization avoids nesting of conditions within schools by each school hosting both conditions, which is feasible given individual program completion. We considered randomization by school, but a group randomized design would require >30 schools to achieve adequate power. Minor concern exists that teens from different conditions may discuss the intervention; as in Project TRAC, we will measure this “cross-talk” via assessment. Project staff will log participants into the password-protected site to avoid outside access. Accessibility will be an ultimate goal of iTRAC, but use will be monitored during the study to control for dose.

Intervention Condition: iTRAC-SRP will consist of eight, approximately 45-minute, “gamified” digital modules of 4-6 activities (games, videos, etc.). Teens will complete modules in after-school supervised groups. Students will be allowed to complete 1-2 modules each week (total intervention completion time 4-8 weeks); project staff will be present at each school at least three days per week, allowing flexible scheduling/attendance. No instruction is needed to use the program. Teens will come to a common area (e.g., classroom, library) where they will be provided a project tablet connected to Wi-Fi. They will have an individual account for the program (password controlled by project staff to prevent outside use), by which they will resume where they left off at the previous module (thus allowing flexible administration and breaks, as needed). We have chosen this strategy for the research for pragmatic reasons; after-school formats are common in schools, and this time, location, and format were successful in TRAC and iTRAC. However, we recognize that the program may be administered differently (e.g., during class time, in waiting rooms, or at home) once it is commercialized.

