Content will use gender- and sexuality-inclusive language and avoids heteronormative descriptions of risk. All modules will include activities that personalize main concepts (some were developed in the pilot). iTRAC’s programming structure does not permit the skipping of content (unless configured to allow it in predetermined instances). Modules will conclude with a quiz (with corrective feedback) that must be passed before moving on.

Waitlist Control Condition: Control participants will be assessed on the same schedule as the treatment condition and offered the intervention after 6-month follow-up. This is an appropriate strategy given that adolescents will still be in the developmental window of early adolescence at the conclusion of the follow-up window, thus the intervention will still be age appropriate.

Fidelity: To preserve internal validity, assurances for consistent delivery will be taken. 1) Research staff complete comprehensive training to assure proper administration, and drift will be monitored through regular team meetings. 2) The computerized nature of iTRAC-SRP will ensure standardized delivery of content. 3) A trained RA will be available to answer questions and problem solve at all appointments. 4) Each module will conclude with a quiz of key content, with corrective information that re-presents concepts relevant to incorrect responses. Participants will not be able to advance to the next module until successfully answering all quiz items. Results will also be saved as data to inform regarding program comprehension. 5) The iTRAC program prevents advancing through video content, to ensure that teens do not skip challenging material. 6) Tracking software will track time spent on each module and activity to assess dose. Summaries of these data (means, ranges) will be reviewed to understand usage patterns that may also inform commercialization.

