Assessment Procedures: Assessments for both conditions will occur at baseline, post-intervention (2 months) and 6 months after baseline. They will minimize participant burden while assessing key constructs of the intervention. Assessments will be administered in a quiet location at school; we expect the battery of self-report and performance measures will take 60-90 minutes. Questionnaires will be administered via tablet, using REDCap to reduce errors and missing values. We will use calendar-aided recall cues and anticipate that recall will be excellent given the salience of risk events for early adolescents. The proposed battery is shorter than that of Project TRAC, which was well-tolerated. Performance measures of emotional competence will be collected via laptop computer. The brief parent battery will be collected via REDCap and can be administered in person, via email link, or, if needed, by phone.

Measures

Primary Outcome: It is well-established that sexual self-efficacy (SSE) is correlated with positive sexual behavior outcomes and sexual well-being among a diverse array of populations¹¹²⁻¹¹⁵. As such, measuring self-efficacy for safer sexual activity as a main outcome will indicate iTRAC-SRP's efficacy and ability to promote healthier sexual behaviors with the full sample (not just those who are sexually active). Adolescents' perceived abilities to engage in behaviors that mitigate sexual risk will be assessed by the Self-Efficacy for HIV Prevention scale (12 items)¹¹⁶. This continuously scaled measure includes items such as "If you decide to have sexual intercourse with your girlfriend/boyfriend, how sure are you that you could talk to your girlfriend/boyfriend about safer sex?" The measure assesses a range of behaviors related to prevention of HIV, other STIs, or unintended pregnancy, including refusing sexual behaviors, discussing sexual histories with partners, buying condoms, taking free condoms, carrying condoms, and asking a partner to use a condom. Participants respond on a 4-point scale (couldn't do it, unsure, sure, very sure). This measure demonstrated good reliability in the TRAC study with this age group ($\alpha = .90$).

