144. Office of Disease Prevention and Health Promotion. *Healthy People 2030*. <https://health.gov/healthypeople/objectives-and-data/data-sources-and-methods/data-sources/national-survey-family-growth-nsfg>

STATISTICAL DESIGN AND POWER

Data preparation: Relevant tests of model assumptions will be evaluated with all analyses, and appropriate corrections for problems in distributions will be implemented. Because even small and statistically non-significant between condition differences in baseline characteristics can adversely affect treatment effect estimates, we will use inverse probability of treatment weights (IPTW) to adjust for potential imbalance between conditions^{1,2}. Covariate balancing propensity scores³ will be used to generate the weights and the model will include demographics and baseline measures of primary outcomes, secondary outcomes, exploratory outcomes, moderators, and mechanisms. The effectiveness of the IPTWs will be evaluated by looking at the average and largest effect sizes for between condition differences prior-to and following weighting. We will also examine the positivity or common support assumption required for IPTW by visually examining the overlap in propensity score distributions for each condition. This assumption is likely to hold in the context of a randomized trial.

Missing data: Based on previous projects, we expect 10% attrition by the end of the 6-month follow-up. We will use fully conditional multiple imputation (a.k.a., multiple imputation using chained equations [MICE]⁴) to address bias introduced by missing data. MICE was selected because it can handle outcomes with different statistical distributions (i.e., binomial, Poisson, normal), it can be applied to a large number of variables, and it has solid performance in simulation studies⁴. This approach assumes data are missing at random (MAR).

Primary Outcome: The primary outcome of the RCT will be Self-efficacy for Sexual Risk Prevention at the 6-month follow-up. All participants who were randomized will be included in all analyses (i.e., intent-to-treat). This outcome will be assessed using an analysis of covariance with baseline included as a covariate.

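### Fixed blocks of 4 let a project recruiter who knows the block size foresee about 29% to 33% of assignments on average; separately, the primary ANCOVA omits school and gender

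*Combined protocol and SAP*

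**What the plan says.** **Allocation.** In Phase 2c, Randomization, students are individually randomized after consent and baseline, and "randomization will be stratified by school and gender and blocked using predetermined size-4 blocks". The same paragraph adds: "Project staff will log participants into the password-protected site to avoid outside access". The allocation ratio and the number of gender categories are not stated. Four schools are named under Human Subjects Involvement and Characteristics.

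**Visibility of arms.** Intervention students use project tablets in supervised after-school groups. For the comparator, Waitlist Control Condition says: "Control participants will be assessed on the same schedule as the treatment condition and offered the intervention after 6-month follow-up".

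**Who recruits.** The Recruitment and Retention Plan (Follow-up Retention, item 4) says: "Each school will have a dedicated research assistant who will assume primary responsibility for recruitment and tracking of participants at that school". The documents do not say who generates or holds the list, how an assignment is released, or whether the block size is withheld from those who recruit.

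**Primary analysis.** Statistical Design and Power, Primary Outcome, specifies: "This outcome will be assessed using an analysis of covariance with baseline included as a covariate". The Data Analysis paragraph of the protocol likewise names only baseline. Under Data preparation, a propensity model for inverse-probability weights is to include demographics and a long list of baseline measures. That may cover gender; school is not named.

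**The concern.** These are two separate matters.

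1. With one fixed block size in an open trial, anyone who knows the size and has watched a stratum fill knows the rest of a block once one arm has used its two places. The person with primary responsibility for recruitment at a school is well placed to have watched. If the next assignment is known, the order in which waiting students complete baseline can be influenced. The primary outcome is self-reported self-efficacy, so steering motivated students to one arm could matter.

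2. Stratified randomization forces the arms to be balanced on school and gender. An analysis that leaves both out does not credit that balance, so its standard error is too large whenever either factor predicts the outcome.

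**Working it through.** **The plan's own figure.** The plan states no figure for predictability. Its power statement is .80 at d = .47 with 120 students, two-sided .05 and r = .6. With 60 per arm and residual SD factor √(1 − .6²) = .8, ANCOVA power is Φ(.47 / (.8 × √(2/60)) − 1.960) = Φ(3.218 − 1.960) = .896 (.891 using the t distribution). The stated .80 is therefore not reproduced, but the difference is on the safe side. The foreseeability result does not use it; it matters only in that the power comparisons below start from about .89.

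**Foreseeable assignments: inputs.** Block size 4, stratification by school and gender, four schools and 120 students come from the documents. Assumed: 1:1 allocation (two of each arm per block), two gender categories (4 × 2 = 8 strata), strata not split by recruitment wave, one-at-a-time release, and an observer who knows the block size and all earlier assignments in the stratum.

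A block has six equally likely orders. By position:

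| Position | Certain in advance | Best guess correct |
|---|---|---|
| 1 | 0 | 1/2 |
| 2 | 0 | 2/3 |
| 3 | 1/3 | 2/3 |
| 4 | 1 | 1 |

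- Complete block: (1/3 + 1)/4 = 33.3% certain.
- Stratum of 15 (three blocks and three further places): 3 × 4/3 + 1/3 = 4.33, and 4.33/15 = 28.9%. Over 8 strata, 8 × 4.33 = 34.7, about 35 of 120.
- Best guess in a stratum of 15: 3 × 2.833 + 1.833 = 10.33, and 10.33/15 = 68.9%.
- Range of the expectation: an incomplete last block costs at most 2/3 of a certain place relative to 33.3%. With 8 strata the minimum is (40 − 8 × 2/3)/120 = 28.9% and the maximum 33.3%. So 28.9% is the lowest expected value for 8 strata, not a ceiling. At 15 per stratum the share in a single trial has a 95% range of 25.0% to 33.3%.
- Sensitivity: 12 strata of 10 would give (40 − 12 × 2/3)/120 = 26.7%.

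**Effect of varying the block size.** Simulation, strata of 15, one-at-a-time release, with sizes 4, 6 and 8 as an illustration: an observer who knows the set of sizes has 2.4% of assignments certain and guesses 66.3% correctly. One who does not know the sizes and only tallies the arms also guesses 66.3% correctly, but is never certain.

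**Omitted stratification factors.** Let R² be the share of baseline-adjusted variance explained by school and gender; the documents give no value, so 0, 5% and 10% are assumed. Because the strata are balanced by design, the baseline-only standard error is too large by about 1/√(1 − R²):

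- R² = 5%: 1/√.95 = 1.026; the effective critical value is 1.960 × 1.026 = 2.011, a two-sided error of 4.4%.
- R² = 10%: 1/√.90 = 1.054; 1.960 × 1.054 = 2.066, error 3.9%.

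Simulation of the ANCOVA (n = 120, r = .6, complete data, unweighted, 40,000 runs) agrees:

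| R² | Error, baseline only | Error, with school and gender | Power at d = .47, without → with |
|---|---|---|---|
| 0 | 5.1% | 5.1% | .889 → .888 |
| 5% | 4.5% | 5.1% | .893 → .902 |
| 10% | 4.0% | 5.1% | .899 → .917 |

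A check that added inverse-probability weights using gender but not school showed a similar pattern. The full planned weighting model was not simulated.

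**The case against.** **Opportunity is small.** Randomization follows consent and baseline, and eligibility is largely objective. Exploiting a known place needs at least two students of the same gender and school waiting at once, plus knowledge of the block size. All of this stands, and it limits the point to an opportunity. A reader might infer that bias is likely, or that a false-positive rate could be attached; the documents give nothing to compute either.

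**Who could exploit it.** A reader might take this to be about school employees. It is not: their involvement ends once permission to contact is given, and they have no access to study records. The people concerned are project staff. That they see earlier assignments is inferred from their roles; no section says they hold the list or perform the randomization.

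**Varying the size hardly reduces guessing.** Correct: best-guess accuracy goes from 69% to 66%. Releasing fixed blocks of 4 in pairs would cut it further, to 57.8%, but leave 15.6% certain. The two measures do different jobs, so the fix includes both, with pooling limited to students who complete baseline on the same day.

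**Is pooling ruled out by timing?** A reader might infer only about five days of slack, since the plan says "Assessments for both conditions will occur at baseline, post-intervention (2 months) and 6 months after baseline" and the modules may take up to eight weeks. That does not follow: no visit window is given, completion may take as little as four weeks, and the primary outcome is at 6 months. Nor can one count how many certain places a recruiter could use. That needs arrival patterns and waiting times, and enrollment in "two waves of enrollment over an eight-month period that will span across two school years" gives no basis for assuming even arrivals.

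**The analysis gap is conservative.** Also correct. A reader might infer that omitting the factors inflates type I error; it does the opposite. The gain is small, and the weighting may already capture gender, so school is the clearer gap.

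**Conclusion.** Both points hold, at modest size.

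1. Under the assumptions listed, an observer with the block size and the earlier assignments foresees on average about 29% to 33% of assignments with certainty. This is a limited opportunity for selection bias, made avoidable by a published fixed block size and silence on concealment and release.

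2. The primary ANCOVA omits both stratification factors. If they explain 5% to 10% of the baseline-adjusted variance (an assumption), the actual error is about 4.5% to 4.0% and about 1 to 2 points of power are lost. If they explain nothing, nothing is lost.

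The case for acting rests on the low cost. The title-page note says Phase 2 is not part of the current submission, which lowers urgency and means nothing has to be undone.

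**What to change.** **Edit 1 (Phase 2c, Randomization).** Replace the blocking clause with: *allocated 1:1 in permuted blocks of randomly varying size. The block sizes and the list are held outside the recruiting team in a separate document and withheld from all project staff who recruit, enroll or track participants. Each assignment is released centrally only after baseline is complete; students in the same stratum who complete baseline on the same day are released together.* Do not print the block sizes in the protocol, since that would defeat withholding them. The sponsor should confirm that 1:1 is intended.

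Effect: certain assignments fall from about 29% to about 2% or less; guessing is only slightly reduced. Cost: a different list, and a possible within-stratum imbalance of 4 instead of 2 if the largest block is 8. With the illustrative sizes, the mean overall arm-size difference rises from 2.2 to 2.5 students, with a 95th percentile of 6 either way.

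**Edit 2 (Statistical Design and Power, Primary Outcome, and the matching sentence in Data Analysis).** Specify the ANCOVA *with baseline, school and gender as covariates*. Cost: 4 degrees of freedom (3 for school, 1 for gender), about 0.1 point of power if neither factor predicts the outcome.
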